1.8 SAMPLE SIZE

1.8.1 HHS – primary endpoint

The primary endpoint will be collected among children aged 12-23 months included in the endline HHS about 12 months after the baseline HHS. Based on a baseline measles vaccination (i.e. at least one dose) coverage reported on vaccination card of 30%⁴, a power of 90%, and an intra-cluster correlation of 0.2, an alpha risk of 5%, it will be necessary to include 74 children per cluster. With a rate of unusable data of 5%, we will need 78 children per cluster or a total of 1,560 children to demonstrate a minimum of +10% points difference between the NutriVax and the standard EPI arms, in measles vaccination coverage, i.e. the primary outcome. This calculation was performed using the Shiny CRT calculator used specifically to estimate sample size for cluster randomised trials⁵.

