2.2 STATISTICAL APPROACH

Variables will be described overall, by arm, by arm and by LGA, by arm and by cluster using appropriate summary statistics for the variable type. For quantitative variables, means, standard deviations, medians, interquartile ranges, and ranges values will be given. Data may be transformed or normalized as necessary based on review of the data distribution.

For qualitative variables, absolute numbers and percentages will be given, and 95% binomial proportion confidence intervals (CI) will be calculated; the exact method will be used when appropriate.

Categorical and discrete data may be aggregated into classes depending on frequency. Statistical testing between arms or subgroups will be carried out using the appropriate statistical test for the variable type (χ^2 , corrected χ^2 or the Fisher's exact test for categorical variables, depending on the observed frequencies and Student's t test, Kruskal Wallis test or the Wilcoxon test, depending on the distribution for continuous variables).

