2.3.2 Type I error

We will use a two-sided type I error α of 5% to compare endpoints between arms without any correction for multiple comparisons.

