3.3 BASELINE RESULTS DESCRIPTION

At the end of the HHS baseline cross-sectional survey, all primary and secondary endpoints will be described at cluster level.

Individual characteristics will be described between arms to assess for sample representativity and possibly identify imbalances. Since the allocation of clusters between arms is carried out randomly, it is known that any differences that do occur must have occurred by chance. This means that the null hypothesis is known to be true, so there is no logic in testing it. The point of displaying between-arm comparisons is not to carry out a significance test, but to describe in quantitative terms how large any differences were.^{9(p200)}

We will use the findings of the baseline analysis to decide which variables need to be adjusted for in the final analysis.

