- Number of days with no cold chain;
- Number of days of stock of measles vaccines in classes.

It will be performed to identify individual and contextual factors associated with measles vaccine coverage.

3.4.1.2 Main analysis second intention:

In second intention, in case the model does not converge due to low numbers of clusters, we will use the cluster-level analysis. Individual data will be aggregated by cluster as summary statistics for a cluster-level analysis approach with a Student or Wilcoxon test depending on the endpoint distribution to determine the intervention effect.^{9(p197),15}

Assumptions will be verified and alternative approach will be considered in case assumptions are not met.

3.4.1.3 Sensitivity analysis:

We are planning to perform the following two sensitivity analyses:

1) Difference-in-difference (DiD) analysis

To provide a robustness check for the results, a difference-in-difference (DiD) analysis will be performed as an impact analysis.

This DiD analysis calculates the effect of the intervention on the outcome by comparing the average change over time in the outcome variable for the intervention arm to the average change over time for the control arm.

DiD focuses on estimating the average treatment effect by comparing changes over time.

The DiD estimate will be calculated using a logistic regression with the period, the arm and an interaction between period and arm as covariates. We will also adjust on selected covariates. Results of DiD in percentage points (pp) and in relative odds ratio (ROR) (with 95% CI) will be reported.

Should the main analysis and this DiD analysis yield to similar findings, that will increase confidence in the validity of our conclusions.

2) Sub-group analysis

Excluding children aged 21-23 months in the cross-sectional household surveys.

This sensibility analysis is planned because these children could have one dose of measles vaccine, but administered before the intervention period.

3.4.2 Analysis of the main secondary endpoint:

The main secondary endpoint is the measles vaccine coverage, defined as the proportion of children aged 6-12 months at inclusion in the longitudinal follow-up survey, who have received at least one additional dose of measles vaccine, as reported on their vaccination card, administered between inclusion and the end of follow-up.

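### The difference-in-difference check is specified with no allowance for wards, so its confidence interval has the wrong width, in a direction set by a correlation that the SAP does not state

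*SAP*

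**What the plan says.** Section 3.4.1.3 offers the DiD as a robustness check on the primary result. The model is given in one sentence: "The DiD estimate will be calculated using a logistic regression with the period, the arm and an interaction between period and arm as covariates". The SAP adds that selected covariates will be adjusted for. The result is to be reported in percentage points and as a relative odds ratio, with a 95% CI. Agreement with the main analysis is to be read as raising confidence in the conclusions.

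The main model in section 3.4.1.1 is a mixed logistic regression with a ward random intercept and a Kenward-Roger correction. The frailty Cox model (3.4.2.2), both additional binary models (3.4.2.4.1 and 3.4.2.4.2) and the anthropometric model (3.4.3.1) each name a ward term. The DiD names none.

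Section 2.2, on general description, plans summaries overall, by arm, by arm and LGA, and by arm and cluster. For proportions it says "95% binomial proportion confidence intervals (CI) will be calculated; the exact method will be used when appropriate".

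**The concern.** Children are sampled within 20 randomised wards, and the same wards are surveyed at baseline and endline. The sampling error of a DiD therefore includes ward-specific change between the two surveys. An ordinary logistic regression does not see that change. It also takes no credit for the stable part of the ward effect, which cancels in the difference. A programmer who follows section 3.4.1.3 literally gets an interval that is correct only by coincidence.

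The SAP relies on this analysis to support or question the primary result. If its CI is too narrow, chance drift in a few wards can look like a confirmed effect, or like a conflict with the main model. The DiD is also where the SAP promises an effect in percentage points, since section 3.4.1.1 reports only a cluster-specific odds ratio. No method is given for obtaining the percentage-point figure, or its CI, from the logit model.

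**Working it through.** **Inputs from the SAP.** 20 wards allocated 1:1, so J = 10 per arm (sections 1.6 and 1.7). Section 1.8.1 gives "an intra-cluster correlation of 0.2", 30% coverage by card, a 10-point difference, 90% power, 74 children per ward and 78 after 5% unusable data. Alpha is two-sided 5% (section 2.3.2).

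**Assumed input.** CAC, the correlation between a ward's baseline and endline effects. The SAP states none, so a range is shown.

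**Step 1: the SAP's own figure.**
- Individually randomised size for 30% versus 40% at 90% power, unpooled variance: 472.8 per arm.
- Baseline-adjusted design effect: [1+(m−1)ρ](1−r²), with r = mρ·CAC/[1+(m−1)ρ].
- At m = 74, ρ = 0.2, CAC = 1: 1+73×0.2 = 15.6; r = 14.8/15.6 = 0.949; design effect 1.559.
- Effective size 740/1.559 = 475 per arm, enough for 472.8.
- 74/0.95 = 77.9, so 78; 78×20 = 1,560.

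The stated size is reproduced at CAC = 1. At CAC = 0.99 the same formula needs 91 per ward.

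**Step 2: variance of the DiD.** With outcome variance σ²:
- Naive (independent children): 4σ²/(Jm).
- True: 4σ²/(Jm) × [1+(m−1)ρ − mρ·CAC].
- Ratio true/naive: (1−ρ) + mρ(1−CAC).

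At m = 78 and ρ = 0.2 this is 0.8 + 15.6(1−CAC). Actual type I error at nominal 5% is 2[1−Φ(1.96/√ratio)].

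| CAC | Variance ratio | SE ratio | Type I error |
|---|---|---|---|
| 1.0 | 0.80 | 0.89 | 3% |
| 0.95 | 1.58 | 1.26 | 12% |
| 0.9 | 2.36 | 1.54 | 20% |
| 0.8 | 3.92 | 1.98 | 32% |
| 0.7 | 5.48 | 2.34 | 40% |

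The ratio equals 1 when 15.6(1−CAC) = 0.2, that is at CAC = 0.987.

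**Step 3: simulation on the logit scale.** With m = 74 and 4,000 simulated trials per setting, the SE ratio was 0.90, 1.29, 1.59 and 2.06 at CAC 1, 0.95, 0.9 and 0.8. Type I error was 2.9%, 12.5%, 21.4% and 33.3%. This agrees with the formula and is slightly larger below CAC 1.

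**Step 4: dependence on the ICC.** At CAC 0.8 and m = 78, ICC 0.1 gives √(0.9+1.56) = 1.57 and ICC 0.05 gives √(0.95+0.78) = 1.32. A lower ICC shrinks the problem but does not remove it.

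**Step 5: by-arm coverage intervals (section 2.2).** For one survey the design effect is 1+77×0.2 = 16.4, and √16.4 = 4.05. At 30% coverage and 780 children per arm:
- naive half-width 1.96×√(0.21/780) = 3.2 points;
- allowing for wards 3.2×4.05 = 13.0 points, or about 15 with a t reference on 9 df (13.0×2.26/1.96).

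At ICC 0.05, 0.1 and 0.3 the factor is 2.2, 2.95 and 4.9.

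**The case against.** Five points can be made for the SAP.

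**The omission may be only brevity.** The sentence lists covariates, which are fixed terms, and it sits under a section whose model has random effects. That is possible. But the adjusted analyses in 3.4.1.1 repeat the random effects explicitly and the DiD does not, so the text as written does not secure a ward term.

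**The error may be harmless.** The sample size is reproduced at CAC 1, where the plain DiD is slightly conservative. This stands, and it is why inflated false positives cannot be presented as what the plan will certainly produce. But CAC 1 means no ward-specific change over a year beyond sampling error, and the direction reverses at 0.987.

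**The factor of 4 is not the DiD's.** A reader might attach it to the DiD. It belongs to single-survey by-arm figures. The DiD reaches it only at CAC 0, which nothing in the SAP suggests.

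**Section 2.2 is general text.** It says "Statistical testing between arms or subgroups will be carried out using the appropriate statistical test for the variable type", and a reader might infer that endpoints will be compared by chi-square on individual children, with type I error near 63%. The SAP does not support that. Section 3.4 and Table 2 send the vaccination and anthropometric comparisons to ward-aware models, and the Student and Wilcoxon fallbacks act on ward summaries. Nor is there a serious conflict at baseline: section 3.3 says of the baseline null hypothesis "so there is no logic in testing it", and that specific rule governs. Section 3.2 openly declares unadjusted baseline summaries. What remains is the binomial interval for coverage by arm and overall.

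**The DiD is one sensitivity analysis.** True. The primary odds ratio comes from a ward random-intercept model with a small-sample correction and is untouched. The omission mainly affects the DiD interval rather than its point estimate.

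**Conclusion.** The concern holds for the DiD and should be fixed before analysis, though it does not threaten the primary result. As specified, the DiD has no term for wards, and its CI is right only if CAC happens to lie near 0.987. At the planning ICC of 0.2 and 78 per ward, the SE ratio runs from 0.89 at CAC 1 to 2.34 at CAC 0.7, with type I error from about 3% to about 40%. These figures rest on equal ward sizes, the planning ICC, a normal approximation and an assumed CAC range; the SAP gives no value that would settle the direction.

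The lesser point also holds: binomial intervals for coverage by arm are too narrow by about 4 at ICC 0.2, and overall figures ignore wards in the same way. Intervals for a single ward do not suffer from this between-ward problem.

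**What to change.** - **DiD model.** In section 3.4.1.3, specify a mixed logistic regression with random intercepts for ward and for ward-by-period and a stated small-sample df method. Alternatively, compare ward-level changes between arms, with 10 wards per arm. A ward intercept alone would still miss ward-specific drift between surveys.
- **Percentage points.** State that the percentage-point DiD and its CI come from ward-level changes or from resampling whole wards.
- **Section 2.2.** Use ward-adjusted CIs for coverage by arm and overall. State that between-arm endpoint comparisons come only from the section 3.4 models, and that the tests listed in 2.2 are not applied between arms to individual-level data.

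The cost is SAP wording and minor programming, with no new data. Coverage intervals will be wider, and the DiD interval will widen or narrow according to how far wards drift.

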1.8.2 LS - Main secondary endpoint

The main secondary endpoint will be collected among the children aged 6-12 months at baseline included in the LS. Based on the baseline measles vaccination coverage reported on vaccination card of 30%⁴, a power of 80%, and an intra-cluster correlation coefficient of 0.2, an individual auto-correlation of 50%, an alpha risk of 5% and a rate of unusable data of 5%, it will be necessary to include 30 children per cluster or 600 children in total to demonstrate a minimum of +10% points difference between arms in measles vaccination coverage. This calculation was performed using the Shiny CRT calculator used specifically to estimate sample size for cluster randomised trials⁵.

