The original Statistical Analysis Plan planned an individual-level longitudinal mixed-effects logistic regression without a random effect at the patient level, thus not accounting for within-subject correlation that was anticipated in the sample size calculation. Even if a patient-level random effect were introduced, the outcome corresponds to an irreversible event (first additional dose of measles vaccine), resulting in a monotonic outcome pattern over time. In this context, the intra-individual correlation is largely non-identifiable, limiting the interpretability and appropriateness of a longitudinal binary GLMM.

Therefore, the primary analysis will use a time-to-event approach, with time since inclusion as the time scale and a shared frailty term for clusters. This approach provides a statistically valid and clinically interpretable estimate of the intervention effect while appropriately accounting for clustering and censoring.

The time-to-event analysis allows a more informative assessment of the intervention effect by incorporating the timing of vaccination, while preserving the original study objective of improving measles vaccine coverage during follow-up.

For completeness, the following additional analyses will be performed:

- A binary end-of-follow-up analysis (event yes/no at the end of follow-up) will be conducted as a sensitivity analysis for descriptive purposes only.
- A longitudinal repeated binary GLMM with a patient-level random effect will be conducted as a secondary exploratory analysis, acknowledging that the intra-individual correlation is largely absorbed by the monotonic outcome pattern.

These additional analyses are not intended to challenge the conclusions drawn from the primary time-to-event analysis.

This approach ensures consistency between the study design and the statistical methods, while preserving the study objectives, endpoints, and sample size assumptions. The original sample size calculation was based on the cumulative incidence of vaccination during follow-up. The time-to-event analysis targets the same cumulative process while using additional information on the timing of vaccination, and therefore does not compromise statistical power.

This amended Statistical Analysis Plan was finalised prior to database lock and before any comparative analysis was conducted.

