3.4.2.1 Description

We will describe at each visit, globally and by age classes at inclusion ([6-9[months, [9-12] months):

- proportion of measles vaccine dose 1,
- proportion of measles vaccine dose 2,
- proportion of patients of at least one additional dose of measles vaccine.

For children included at [6-9[months old, measles vaccine dose 1 is supposed to be administered before the first follow-up visit (i.e V1) occurring 4 months after inclusion (i.e M4); measles vaccine dose 2 is supposed to be administered before V2 (M8) if included at [7-9[months old or before V3 (M12) if included at [6-7[months old.

For children included at [9-12] months old, measles vaccine dose 1 is supposed to be administered before inclusion, and measles vaccine dose 2 is supposed to be administered before V1 (M4) if included at [11-12] months old or before V2 (M8) if included at [9-11[months old.

3.4.2.2 Main analysis first intention:

In first intention, analysis will be conducted at the individual level, adjusting for clustering.

A time-to-event approach will be used, where time is defined from inclusion to the first occurrence of an additional dose of measles vaccine. A shared frailty model (Cox proportional hazards model with a random intercept for cluster)^{16,17} will be used to estimate the effect of the intervention.

The intervention effect will be estimated as a hazard ratio (HR) with 95% confidence intervals, comparing the instantaneous risk of receiving an additional dose of measles vaccine between the intervention and control arm, accounting for clustering via the shared frailty term.

For interpretability, the cumulative incidence of vaccination at 12 months will be estimated from the shared frailty Cox model and reported by study arm, together with the absolute difference between arms. Kaplan–Meier curves will be used for descriptive visualization only.

This approach appropriately accounts for clustering, the timing of vaccination, and censoring, and provides a statistically valid and clinically interpretable estimate of the intervention effect.

No adjustment for baseline vaccination status is planned, as the expected number of doses depends on age at inclusion (for children aged 6–9 months at inclusion, 0 dose is expected).

The variance of the shared frailty term will be reported to describe the between-cluster variability.

Adjusted analyses

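### The longitudinal sample size in SAP 1.8.2 does not fit the frailty Cox analysis in 3.4.2, so the statement that power is not compromised is unsupported; on the plan's own inputs power is far below 80%

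*SAP*

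**What the plan says.** SAP 1.8.2 sizes the longitudinal survey at 30 children per ward, 600 in all. It starts from a coverage level ("Based on the baseline measles vaccination coverage reported on vaccination card of 30" per cent), assumes "a power of 80%, and an intra-cluster correlation coefficient of 0.2", adds "an individual auto-correlation of 50%, an alpha risk of 5% and a rate of unusable data of 5" per cent, and aims "to demonstrate a minimum of +10% points difference between arms in measles vaccination coverage".

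SAP 3.4.2 replaces the earlier longitudinal logistic model with a shared-frailty Cox model. It says the sample size assumptions are preserved and makes two statements about power. The first is "The original sample size calculation was based on the cumulative incidence of vaccination during follow-up". The second is that the new analysis targets the same cumulative process "while using additional information on the timing of vaccination, and therefore does not compromise statistical power".

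SAP 3.4.2.2 specifies the main model: arm effect, ward frailty, time from inclusion to the first additional dose. It adds: "No adjustment for baseline vaccination status is planned, as the expected number of doses depends on age at inclusion". No small-sample correction or reference distribution is named for this model. The primary model (3.4.1.1) and the anthropometric model (3.4.3.1) both carry a Kenward-Roger correction because the clusters are few.

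**The concern.** An individual auto-correlation has meaning only when the same child's outcome is measured at least twice. A cumulative-incidence comparison has no place for it. Section 3.4.2 itself acknowledges that the sizing anticipated within-subject correlation, so its later description of the calculation conflicts with its own text as well as with 1.8.2.

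The endpoint is a dose given after inclusion. Every child therefore starts at zero, and there is no individual baseline outcome to correlate with the final one. If the 80% came from the baseline terms, it does not carry over to the main Cox model.

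What is at stake is how a null result on the main secondary endpoint is read. Sections 3.4.2 and 3.4.2.4 say that discordant supporting analyses will not affect the conclusions. A reader told that power is intact could then take a non-significant hazard ratio as evidence of no effect.

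**Working it through.** **Inputs.** From 1.8.2: 30% versus 40%; ICC ρ = 0.2; individual auto-correlation IAC = 0.5; 5% unusable data, so 30 × 0.95 = 28.5 usable per ward. From 1.6 and 1.7: 20 wards, 1:1, so k = 10 per arm. From 2.3.2: two-sided α of 5%. Derived: σ² = (0.3×0.7 + 0.4×0.6)/2 = 0.225. Not stated in the SAP: the ward (cluster) auto-correlation, CAC.

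**1. Reproducing 30 per ward.** For a cohort with a baseline period:

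- V = [2σ²/(k·m)] · [1+(m−1)ρ] · (1−r²)
- r = [m·ρ·CAC + (1−ρ)·IAC] / [1+(m−1)ρ]
- power = Φ(0.10/√V − 1.96)

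With CAC = 1 and m = 28: 1+27×0.2 = 6.4; r = (5.6+0.4)/6.4 = 0.9375; 1−r² = 0.1211; V = (0.45/280)×6.4×0.1211 = 0.001246; SE = 0.0353; power 80.9%. At m = 27 power is 79.5%. So m = 28, and 28/0.95 = 29.5, which rounds to 30 per ward as stated. At 28.5 usable, power is 81.5%.

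The same formula with CAC = 1 and no individual term gives 90.1% at 74 per ward, matching 1.8.1. Two stated figures reproduce, which makes CAC = 1 a fair inference.

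**2. Sensitivity to the unstated CAC.** At 28.5 per ward, still with baseline and IAC 0.5:

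| CAC | SE | Power |
|---|---|---|
| 1 | 0.0350 | 81.5% |
| 0.95 | 0.0453 | 60% |
| 0.9 | 0.0532 | 47% |
| 0.8 | 0.0655 | 33% |

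**3. Removing the baseline.** Without the factor (1−r²), V = (0.45/285)×6.5 = 0.01026 and SE = 0.101. Power is 16.5% by the normal formula above (16.7% counting both tails), and 14.0% to 15.5% with t on 18 df, depending on the approximation. With unlimited children per ward, V tends to 2σ²ρ/k = 0.45×0.2/10 = 0.009, SE = 0.095, and power stops at about 18%. The difference detectable with 80% power is about 2.80×0.101 = 0.28, or 28 points.

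**4. Does event timing change this?** A shared-frailty time-to-event simulation (constant hazard, gamma frailty, ICC of 12-month incidence averaging 0.2, conditional hazard ratio 1.52, 28 per ward, 1,500 runs) gave 18% with t on 18 df and 21% with a Wald z test. That z test rejected 8% of the time under the null.

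Ignoring clustering altogether, the hazard ratio is ln 0.6/ln 0.7 = 1.432, with 285×0.3 + 285×0.4 = 199.5 events. Then z = ln(1.432)×√199.5/2 = 2.54 and power is about 72%, against 71% for two proportions. Timing adds little at these inputs.

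**5. Range over ICC**, no baseline, 30% versus 40%, normal approximation:

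| ICC | Design effect | Power |
|---|---|---|
| 0.20 | 6.5 | 16.5% |
| 0.10 | 3.75 | 26% |
| 0.05 | 2.375 | 37% |
| 0.02 | 1.55 | 52% |
| 0.01 | 1.275 | 61% |
| 0 | 1 | 71% |

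**6. Adding ward baseline coverage.** If it explains a share R of between-ward variance, V = (2σ²/k)·[ρ(1−R) + (1−ρ)/m]. For R = 0.5: 0.045×(0.1+0.0281) = 0.00576, SE 0.076, power 26% (24% with a t reference). For R = 0.9: 0.045×(0.02+0.0281) = 0.00216, SE 0.047, power 58% (53% with t). R is an assumption; the SAP gives no value.

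**7. Small-sample inference.** P(|t| > 1.96) on 18 df is 6.6%.

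**The case against.** The strongest reply is that the amendment did no harm. Section 3.4.2 says the superseded model had no patient-level random effect and so already ignored the correlation used in the sizing. Whether that model adjusted for baseline is not shown. If no individual baseline gain exists for this endpoint, 80% was never attainable and the fault lies in 1.8.2. Against a binary end-of-follow-up analysis with the same ward effect, using event times should not lose power. All of this stands. A reader might infer that the change to Cox took power from 80% to 16%, and the document does not support that. It supports only that 1.8.2 and 3.4.2 do not match.

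A reader might also take 16% as the power of the trial's analysis. That figure applies ICC 0.2 and 30% versus 40% to the 12-month incidence of an additional dose, for which the SAP gives no separate values. Section 1.8.3 allows both estimates to be revised after the baseline survey.

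The proposed covariate measures a different thing: at least one dose in children aged 12–23 months. The adjusted frailty model in 3.4.2.2 already includes age, distance, cold chain and vaccine stock. That model might recover some power, but it is not the first-intention analysis and omits ward baseline coverage.

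Finally, the SAP does not say which reference distribution the Cox model will use, so the 6.6% applies only if a normal cutoff is used. The hazard ratio's confidence interval would show imprecision to a careful reader.

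**Conclusion.** The two power sentences in 3.4.2 are wrong as written. The first misdescribes the calculation in 1.8.2. The second attaches the 80% to a model without the terms that produce it.

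On the plan's inputs, the main analysis has about 15–20% power at ICC 0.2 across the proportion and hazard scales. No ICC reaches 80%, since even without clustering power is about 71%. This is conditional on 30% versus 40% as the 12-month incidence and on 28.5 usable children per ward; other incidence levels would give other figures. The 81.5% comparison rests on CAC = 1, which the SAP does not state.

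The finding concerns the main secondary endpoint only. The primary model adjusts for ward baseline coverage and carries a small-sample correction, so nothing here weakens it.

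**What to change.** 1. In 3.4.2, delete both power sentences and the claim that the sample size assumptions are preserved. State the power of the Cox analysis over a range of ICC and 12-month incidence, marked as conditional on those assumptions. Say that 1.8.2 sized a different design and give the ward auto-correlation it used.
2. In 3.4.2.2, add the ward's baseline measles coverage as a covariate in the main frailty model. Section 3.1.2 already computes it and provides for assigning it to every participant of a ward, and 3.4.1.1 uses it. The reason given for not adjusting concerns a child's own dose count and does not apply to a ward-level measure.
3. Take the p-value and confidence interval from a t reference with between-ward degrees of freedom, or from a ward permutation test stratified by LGA.

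The cost is SAP wording, a covariate already in hand, a few lines of code and one between-ward degree of freedom (18 to 17). The stated power becomes less favourable and stays below 80% even with the covariate. The change should be made before any comparative analysis.
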